## 2.0 Rationale and Specific Aims

### Specific Aim 1 -

To test the hypothesis that enteral supplementation of L-citrulline (a precursor of Larginine) is effective in increasing plasma L-arginine and L-citrulline concentrations in premature infants with increased NO production.

Intervention: Enteral L-citrulline supplementation

Rationale & feasibility - L-arginine is a precursor of NO production. Premature infants who develop BPD\_PH have lower levels of L-arginine and L-citrulline, decreased NO production, eventually leading to the development of pulmonary hypertension. Oral arginine is poorly bioavailable hence oral L-citrulline will be used (precursor of L-arginine, see figure below). We expect L-citrulline supplementation in premature infants will increase plasma L-arginine and L-citrulline concentrations and increase NO production (measured indirectly by urinary end-products).

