### 4.0 Treatment Assignment/Randomization

**Recruitment** - Parents of all eligible infants will be approached by research investigator to discuss about the study & research protocol in detail. All questions & concerns will be answered in very simple language & parents will be given written consent form to read. Within 24 to 48 hours, the parents will be approached again to discuss & explain any question they have. We expect around 70 - 75% success in the recruitment. Every year, we deliver around 50 infants ( $\leq$ 30 weeks' gestation). We hope to recruit our desired sample of 42 infants (14 in each study group) within 12 months.

**Sample size:** 14 preterm infants will be randomized to each group (total sample 42) A sample size of 14 at each group (low, median, and high dose) for efficacy endpoint will reach a power of 0.80 to detect an effect size of 0.5 based on one-way ANOVA with a 0.05 significance level. A sample size of 11 at each group for safety endpoint will reach a power of 0.92 at a 0.05 significant level for an equivalence test of means using two onesided tests, when the true difference between the means is 0.0 mmHg, the standard deviation is 10.0 mmHg, and the equivalence limits are -15.0 mm Hg and 15.0 mmHg.

**Randomization:** Adaptive randomization method will be used – each new participant will be sequentially assigned to a particular treatment group by taking into account the previous assignments of participants. For example, first recruit will be Group 1, second Group 2, third Group 3, fourth Group 1 and so on. The study will be blinded to the nurses and parents. If patients complete 12/14 doses of the treatment, they will be analyzed in the treatment arm.

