### 9.0 Statistical Considerations

Study design: Single-center Pilot dose-ranging study

Study population: Premature infants admitted to the Neonatal intensive care unit at UTMB, Galveston.

Rationale: L-citrulline has been shown to increase NO production in neonatal pigs. The use of L-citrulline in premature infants may help increase NO and prevent pulmonary hypertension that develops due to chronic lung disease. Even though L-citrulline has been used safely in infants and children for urea cycle disorders, its dosage, efficacy and safety have not been evaluated in premature infants. Therefore, a pilot dose-ranging study is essential.

There will be 3 study groups in this Phase I trial:

Group 1 (Low dose): 100 mg/kg/day of L-citrulline Group 2 (Medium dose): 200 mg/kg/day of L-citrulline Group 3 (High dose): 300 mg/kg/day of L-citrulline

Sample size: A sample size of 14 at each group (low, median, and high dose) for efficacy endpoint will reach a power of 0.80 to

detect an effect size of 0.5 based on one-way analysis of variance (ANOVA) with a 0.05 significance level. The sample size calculation was based on the following expected mean  $\pm$  SD citrulline concentrations in plasma according to the study from Schwedhelm et al:

Low dose group:  $19 \pm 4 \ \mu mol/L$ Medium dose group:  $21 \pm 4 \ \mu mol/L$ High dose group:  $45 \pm 5 \ \mu mol/L$ 

Primary outcome:

1. Increase in plasma L-citrulline levels and increased NO production (measured indirectly via urinary breakdown products)

Secondary outcomes:

- 1. To determine safety of enteral L-citrulline supplementation in premature infants.
- 2. To determine the dose of enteral L-citrulline needed to increase plasma level of citrulline > 37 mol/L.

Data will be collected from electronic medical records. Measurements will be recorded in a password protected computer on an excel sheet.

A Data Safety Monitor Board (DSMB) as mentioned in section 7.0 will be reviewing safety data every 4 months.

The data will be analyzed at the end of data collection for all subjects who meet the inclusion criteria. SPSS version 24 will be used for data analysis. SAS procedures, linear models, repeated measures analysis of variance (ANOVA) & logistic modeling for receiver operator curve generation (significance p<0.05) will be used. The UTMB Clinical trials studio will be involved to assist in statistics.

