# Procedure for accounting for any missing, unused and spurious data:

In this pilot study, subjects with missing data on important predictors (lack of blood sample for serum arginine/citrulline levels) will be excluded from analyses.

Selection of subjects to be included in the analyses:

We will follow an intention-to-treat approach in the analyses. The primary variables (plasma arginine, citrulline levels and urinary nitrite, nitrate levels) are continuous data

and the one-way ANOVA will be used to analyze differences amongst the 3 treatment groups from day 0 and day 7. Paired T-test will be used to evaluate differences pre-and post-treatment in individual subjects. The data gathered from daily urinary nitrite and nitrate measurements will be represented in line graphs to represent the trend.

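### The primary outcome is defined in two different ways with no success rule, while the 0.80 power and 5% error rate hold only for one ANOVA of one variable

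*Combined protocol and SAP*

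**What the plan says.** Section 9.0, under the primary outcome, has one numbered item: "Increase in plasma L-citrulline levels and increased NO production (measured indirectly via urinary breakdown products". It has two parts joined by a conjunction, and arginine is not among them.

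Further on in Section 9.0, where the plan selects subjects for analysis, the list is longer: "The primary variables (plasma arginine, citrulline levels and urinary nitrite, nitrate levels) are continuous data". A one-way ANOVA across the three doses is assigned to these variables, and paired t-tests are planned for pre-to-post differences. The significance level in Section 9.0 is 0.05.

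Specific Aim 1 (Section 2.0) gives a third version, that supplementation "is effective in increasing plasma L-arginine and L-citrulline concentrations in premature infants with increased NO production". The dosing justification in Section 4.0 gives a fourth. It describes efficacy as a citrulline level above 37 µmol/L together with rises in arginine and in urinary nitrites/nitrates, although Section 9.0 lists the 37 threshold as a secondary outcome.

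The sample size is written for one endpoint. Section 4.0 states that "14 preterm infants will be randomized to each group (total sample 42") and that this "will reach a power of 0.80 to detect an effect size of 0.5". Section 9.0 repeats the claim and adds: "The sample size calculation was based on the following expected mean", followed by means and SDs for plasma citrulline alone. No planning value is given for arginine, nitrite or nitrate.

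**The concern.** A trial with several primary variables needs a rule: all must succeed, any may succeed, or they are tested in a fixed order. The rule decides which error rate and which power apply. This plan has none, and its sections disagree on which variables count.

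The gap could matter in practice. Suppose citrulline rises with dose and urinary nitrite and nitrate do not move. Read as a joint requirement, the primary outcome has failed. If a reader takes any one of the listed primary variables as enough, it has succeeded. With no rule written down, that choice could be made after the data are seen. The Background section says the results will inform a later randomised placebo-controlled trial, so how this one is read has consequences.

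The contrast is also unsettled. The outcome is worded as an increase, which is a pre-to-post question, whereas the power is for differences between doses. Both tests are planned and neither is named primary.

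**Working it through.** **Inputs from the documents.** Three groups of 14 (N = 42), effect size 0.5, one-way ANOVA, alpha 0.05 (Sections 4.0 and 9.0). Expected plasma citrulline 19 ± 4, 21 ± 4 and 45 ± 5 µmol/L (Section 9.0). Four primary variables (Section 9.0, analysis text).

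**1. The plan's own figure.** Reading 0.5 as Cohen's f, the noncentrality is λ = N f² = 42 × 0.25 = 10.5, with 2 and 39 degrees of freedom. The noncentral F distribution gives power 0.803, so the stated 0.80 reproduces for one ANOVA of one variable. Reading 0.5 as f² gives 0.98, and as a largest-minus-smallest standardised difference 0.19, so Cohen's f is what was meant.

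**2. Joint reading: citrulline and NO must both succeed.** Requiring every test to reach 0.05 keeps the overall error rate at or below 5% without adjustment. Only power is in question. *Assumption, not in the documents: f = 0.5 for every variable.*

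| Variables required | Power if independent | Power for correlation 0 to 0.8 (simulated) |
|---|---|---|
| 2 (citrulline, one NO measure) | 0.803² = 0.65 | 0.65 to 0.74 |
| 3 (citrulline, nitrite, nitrate) | 0.803³ = 0.52 | 0.52 to 0.68 |

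Under independence, joint power of 0.80 would take about 18 per group for two variables and 20 for three.

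**3. What the plan's citrulline values imply.** The grand mean is (19 + 21 + 45)/3 = 28.33. The SD of the group means is √[(9.33² + 7.33² + 16.67²)/3] = 11.81. The pooled SD is √[(16 + 16 + 25)/3] = 4.36. So f = 11.81/4.36 = 2.71, and power at 14 per group is essentially 1. On these values joint power equals the power for NO: 0.80 if NO is one measure with f = 0.5, and otherwise unknown, because no mean or SD for nitrite or nitrate is given.

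**4. Any-of-four reading.** With each ANOVA at 0.05, familywise error under independence is 1 − 0.95⁴ = 0.185. By simulation it is about 0.18, 0.16 and 0.12 at common correlations of 0.3, 0.5 and 0.8. At f = 0.5, power for at least one variable is 0.92 or more. With a Bonferroni level of 0.05/4 = 0.0125, power per variable at 14 per group is 0.61, and 0.80 needs 20 per group.

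**5. Counting the paired tests.** The plan does not say whether they are pooled or run by dose group.

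- One pooled paired test per variable makes 8 tests: 1 − 0.95⁸ = 0.34 under independence.
- One per dose group makes 16 tests. Simulating the ANOVA on change with three paired tests on the same data gives a familywise error of about 0.49 with independent variables and about 0.33 at correlation 0.8.

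**The case against.** **Neither figure holds under either reading.** A reader might infer this, and it goes too far. The joint reading keeps the 5% error rate, and the any-of-four reading keeps power above 0.80. Each reading leaves one figure unsupported, so what fails is the pair taken together.

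**Power for the joint outcome is 0.64 or 0.65.** This is tempting but not shown. It gives citrulline f = 0.5, whereas the plan's own means give 2.71. The documents support only that power for the NO component, and therefore for the joint outcome, has not been established.

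**Sixteen tests give 1 − 0.95¹⁶ = 56%.** This does not hold. The ANOVA and the by-group paired tests share the same data, so the product rule does not apply, and the plan does not say that paired tests are run by dose group.

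**The plan contains two competing success rules.** It does not. The analysis text names variables and tests and sets no rule; the any-of-four reading is one way to fill the gap. The weakness is a missing rule together with inconsistent lists.

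**This is a 42-infant, single-centre pilot, and the variables lie on one pathway.** Both are fair. Strict familywise control matters less here, and correlation brings inflation below the independence figure. That argues for a modest remedy. It does not remove the inconsistency, because the plan itself claims 0.80 power at a 0.05 level.

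**Conclusion.** The point stands in this form. Section 9.0 gives two different accounts of what is primary, Specific Aim 1 and the dosing justification differ again, and no all/any or multiplicity rule is stated. The 0.80 power and 5% error rate belong to one ANOVA of one variable, and planning values exist only for plasma citrulline.

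The size depends on the rule chosen:

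- **Both citrulline and NO required:** error stays at or below 5% and power is not established. The 0.65 illustrates it, resting on independence and an assumed f = 0.5 for each.
- **Any of the four ANOVAs sufficient:** familywise error is up to 18.5%, and about 12% at correlation 0.8. It is higher when the paired tests are counted, by an amount that depends on how they are run.

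The true correlations are not in the documents, so the any-of-four figures are a range. The plan should be corrected, in proportion to a pilot.

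**What to change.** Name the change in plasma citrulline from Day 0 to Day 7 as the single primary variable. Using change keeps the increase that the outcome describes; a Day 7 level alone would lose it. Name one primary contrast, the between-dose one-way ANOVA, since that is what the power statement covers.

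Make arginine secondary, together with one pre-defined urinary measure of NO. State how nitrite and nitrate are combined and whether the measure is normalised to the urinary creatinine already being assayed. Report these, and the pre-to-post comparisons, with confidence intervals and no confirmatory claim.

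Use one list in Specific Aim 1, the dosing justification in Section 4.0 and both parts of Section 9.0. State that the 0.80 power applies to citrulline only. Say also that f = 0.5 is a chosen effect size, because the listed means, which are concentrations and not changes, give 2.71.

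The cost is a wording amendment in four places, with ethics approval before use, and no added infants, samples or procedures. The real downside is that NO production becomes secondary. If the sponsor wants it kept as primary, the plan should state that citrulline and NO must both succeed and that the 0.80 does not cover the joint outcome.

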# Procedure for accounting for any missing, unused and spurious data:

In this pilot study, subjects with missing data on important predictors (lack of blood sample for serum arginine/citrulline levels) will be excluded from analyses.

Selection of subjects to be included in the analyses:

We will follow an intention-to-treat approach in the analyses. The primary variables (plasma arginine, citrulline levels and urinary nitrite, nitrate levels) are continuous data

and the one-way ANOVA will be used to analyze differences amongst the 3 treatment groups from day 0 and day 7. Paired T-test will be used to evaluate differences pre-and post-treatment in individual subjects. The data gathered from daily urinary nitrite and nitrate measurements will be represented in line graphs to represent the trend.

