## Specific Aim 3 –

To determine the dose of enteral L-citrulline required to increase plasma level of > 37  $\mu$ mol/L.

We will use three doses (low, medium and high) of enteral L-citrulline as follows -**Group 1**: *Low dose* 50 mg/kg given two times a day (100 mg/kg/day) for total 7 days. **Group 2**: *Medium dose* 100 mg/kg given two times a day (200 mg/kg/day) for total 7 days

Group 3: High dose 150 mg/kg given two times a day (300 mg/kg/day) for total 7 days

Rationale:

Previous studies in patients undergoing cardiac surgery have shown that post-operative pulmonary hypertension did not develop in patients with citrulline level > 37  $\mu$ mol/L(7). A cross-sectional study reported that citrulline levels < 29  $\mu$ mol/L was associated with BPD\_PH (100% sensitivity and 75% specificity) hence this may be used as a screening tool for BPD\_PH(3). We will use the higher levels of citrulline of the reported levels as our goal (>37 $\mu$ mol/L). We will supplement infants with 3 different dosages and check serum levels to see what dose is required for to achieve optimal plasma level of citrulline (>37 $\mu$ mol/L).

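### The between-dose ANOVA does not name its response and leaves the Day 0 value unused as a covariate; ANCOVA on Day 0 would fix the response and modestly narrow the intervals

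*Combined protocol and SAP*

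**What the plan says.** The analysis wording is in section 9.0, in the text on missing data and selection of subjects. It names plasma arginine and citrulline and urinary nitrite and nitrate as continuous primary variables, then gives three methods:

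- Between doses: "one-way ANOVA will be used to analyze differences amongst the 3 treatment groups from day 0 and day 7".
- Within infants: "Paired T-test will be used to evaluate differences pre-and post-treatment in individual subjects".
- Daily urine: "The data gathered from daily urinary nitrite and nitrate measurements will be represented in line graphs to represent the trend".

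Earlier in section 9.0 the primary outcome is "Increase in plasma L-citrulline levels and increased NO production", and the general methods list includes linear models and "repeated measures analysis of variance (ANOVA) & logistic modeling for receiver operator curve generation". None of these is tied to an outcome, a response or a covariate. The sample-size paragraph gives expected plasma concentrations of 19 ± 4, 21 ± 4 and 45 ± 5 µmol/L for the low, medium and high doses.

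Section 5.0 (Sample collection) plans blood on Day 0 and Day 7 and urine on Day 0 and daily thereafter. Section 5.0 (Measurements) adds urinary creatinine.

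On the target level, Specific Aim 3 is "To determine the dose of enteral L-citrulline required to increase plasma level of > 37" µmol/L, to be met by a plan to "check serum levels to see what dose is required for to achieve optimal plasma level of citrulline". The dosing justification in section 4.0 gives the same level as part of its efficacy criterion, and section 9.0 repeats it as a secondary outcome.

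**The concern.** The ANOVA sentence can be read in three ways, and the rest of the plan points in different directions. A primary outcome worded as an increase suggests change; a sample size built on concentrations suggests the Day 7 level. The choice therefore stays open until data are in hand. The two estimates of a dose difference are not interchangeable: they differ by exactly the Day 0 difference between the groups. The Day 0 value, which could sharpen the comparison at no sampling cost, has no stated use as a covariate.

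The neighbouring analyses have smaller gaps. The paired test is not said to be run per dose or pooled. The daily urine series is linked only to graphs. The 37 µmol/L target has no summary measure and no interval. The Background says that this pilot's information will feed a later placebo-controlled trial, so its estimates and intervals are its main product.

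**Working it through.** **Inputs from the plan.** 14 infants per group (N = 42), effect size 0.5, two-sided significance level 0.05, stated power 0.80 (sections 4.0 and 9.0); expected means 19, 21, 45 and SDs 4, 4, 5 µmol/L (section 9.0).

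**Assumed, because the documents do not give them.** The Day 0–Day 7 correlation ρ, shown at 0, 0.3, 0.5 and 0.7; equal SDs on the two days; a Day 0 SD of 2 to 5 µmol/L; three groups that are exchangeable at Day 0.

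**Step 1: the plan's own figure.** Noncentral F with f = 0.5, noncentrality 0.5² × 42 = 10.5 and df 2 and 39 gives power 0.803. The stated 0.80 reproduces, for an ANOVA of the Day 7 level.

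**Step 2: power under each reading at f = 0.5.** For change, f = 0.5/√(2(1−ρ)), df 2 and 39. For ANCOVA, f = 0.5/√(1−ρ²), df 2 and 38.

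| ρ | Day 7 level | Change | ANCOVA |
|---|---|---|---|
| 0 | 0.80 | 0.49 | 0.80 |
| 0.3 | 0.80 | 0.65 | 0.84 |
| 0.5 | 0.80 | 0.80 | 0.91 |
| 0.7 | 0.80 | 0.96 | 0.98 |

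Simulated ANCOVA power (20,000 runs per row) is 0.79, 0.83, 0.90 and 0.98.

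**Step 3: power under the plan's own means.** The overall mean is (19 + 21 + 45)/3 = 28.33. The between-group SD is √[(9.33² + 7.33² + 16.67²)/3] = 11.81. The pooled SD is √[(16 + 16 + 25)/3] = 4.36. So f = 11.81/4.36 = 2.71, and the overall test has power near 1 under all three readings.

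**Step 4: 95% half-width for one dose difference (µmol/L).**
- Day 7: t(0.975, 39) × 4.36 × √(2/14) = 3.3.
- Change: the Day 7 value × √(2(1−ρ)) = 4.7, 3.9, 3.3, 2.6.
- ANCOVA: t(0.975, 38) × 4.36 × √(2/14) × √(1−ρ²) × √(1 + 1/37) = 3.4, 3.2, 2.9, 2.4. The last factor allows for chance Day 0 imbalance. ANCOVA and Day 7 are equally precise at ρ of about 0.17.

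**Step 5: how far the choice can move an estimate.** The change difference equals the Day 7 difference minus the Day 0 difference. For low versus medium the expected difference is 21 − 19 = 2. The Day 0 difference has standard error SD × √(2/14).

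| Assumed Day 0 SD | Standard error | Chance that the Day 0 difference exceeds 2 |
|---|---|---|
| 2 | 0.76 | 1% |
| 3 | 1.13 | 8% |
| 4 | 1.51 | 19% |
| 5 | 1.89 | 29% |

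**Step 6: the paired test.** With equal Day 0 means, a change pooled over doses would lie 28.33 − 19 = 9.3 above the low-dose change and 45 − 28.33 = 16.7 below the high-dose change. Run per dose, the half-width is t(0.975, 13) × 4.36 × √(2(1−ρ))/√14 = 3.6, 3.0, 2.5, 1.9.

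**Step 7: the 37 µmol/L target.** Exact 95% intervals at n = 14 are 0–23% for 0/14, 23–77% for 7/14 and 66–99.8% for 13/14.

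**The case against.** The strongest reply is that little would change in practice. Under the plan's expected means the overall test, which is the only one powered, succeeds whichever response is chosen. That stands: a reader might infer from Step 2 that the trial is underpowered or its power statement wrong, but 0.80 reproduces and f = 2.71 makes power immaterial if the expected means are right.

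The gain from ANCOVA also rests on an undocumented correlation. At 0.3 the interval narrows only from 3.3 to 3.2, and below about 0.17 it is slightly wider. The correlation could be low, since supplementation falls between the two samples. This stands too, and limits the benefit to a modest one.

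A reader might infer that chance imbalance at Day 0 will usually match the low–medium difference. It will not. The average absolute imbalance for that pair is 1.2 to 1.5 µmol/L at SD 4 to 5, and it exceeds 2 in a minority of trials at every SD shown. A difference of 2 is also inside every half-width in Step 4, so this design would not resolve it well under any reading.

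Three further inferences go too far. The paired test is not the only planned test that could address an increase, because repeated measures ANOVA is listed; it is the only one explicitly linked to the outcome. Urine is not confined to graphs, because nitrite and nitrate are among the variables covered by the ANOVA sentence; only the daily series is. And the target is not wholly undefined: variable, threshold and sampling day are stated. On the plan's figures, assuming normality, about 0%, 0% and 94.5% of infants would exceed 37, so mean and proportion point to the same dose.

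None of this supplies the missing response, the use of Day 0, or an interval.

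**Conclusion.** The point holds as a cheap improvement to an under-specified analysis, not as an error that invalidates the trial. The ANOVA response is not defined, and Day 0 is collected but not used as a covariate. At f = 0.5 the reading chosen moves power between 0.49 and 0.98 over the assumed correlations; under the plan's own means it does not matter for the overall test. What is at stake is the estimate and its interval: precision that depends on which response is picked, and a low–medium estimate that shifts by more than its whole expected size in about 1% to 29% of trials for Day 0 SDs of 2 to 5. These figures rest on the assumed correlation, equal SDs, the assumed Day 0 SD and 14 infants per group analysed. The paired-test, urine and target-level gaps are mainly missing detail and carry less weight.

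**What to change.** Replace the ANOVA sentence with: ANCOVA of Day 7 plasma citrulline on dose group, adjusted for the Day 0 value, reporting adjusted dose differences with 95% confidence intervals; likewise for arginine. State that the paired Day 7 minus Day 0 comparison is run within each dose, with a 95% confidence interval. Without an untreated group, that comparison cannot separate a drug effect from a week of maturation or feeding change, and the text should say so.

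Secondary suggestions:
- Analyse daily urinary nitrite and nitrate with a repeated-measures model adjusted for Day 0. Say beforehand whether values are creatinine-corrected and whether the two analytes are combined.
- For each dose, report the number and proportion of infants above 37 µmol/L at Day 7, with an exact 95% interval. The sponsor should state before analysis what proportion it will count as reaching the target; none is proposed here.

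The cost is a paragraph of wording and one error degree of freedom. No new samples are needed. The downsides are slightly lower precision than the Day 7 ANOVA if the correlation is below about 0.17 (3.4 against 3.3 at zero) and wide exact intervals at n = 14. Both would worsen if numbers fall, since infants without a blood sample are excluded (section 9.0) and withdrawals are not replaced (section 8.0).

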In-vitro and In-vivo studies of L-citrulline supplementation in newborn piglets showed increased NO production and decreased PH in newborn piglets. These studies also showed that treatment with L-citrulline reduced superoxide generation, increased NO production as well as helped with eNOS re-coupling which is the active form of eNOS (dimeric form of eNOS is the active form).

**Arginine as essential amino acid:** Under routine conditions arginine is not an essential amino acid but is considered an essential amino acid in neonates, particularly under stress, infection and prematurity. In neonatal period (suckling period), the major source for endogenous arginine biosynthesis is from citrulline in the intestine.

**Source of L-arginine in preterm infants:** Routinely, extremely premature infants receive nutrition as total parental nutrition (TPN i.e. infants get infusion of protein, fat and carbohydrate via central venous line) that contains L-arginine (approximately 1mg/1mL) to metabolize ammonia via urea cycle. PIs receive adequate amount of intra venous arginine from TPN. Routinely, PIs are started with small volumes of enteral feeds which are increased slowly overtime. TPN is slowly decreased as enteral feeds are increasing. As the TPN is going down, intra venous L-arginine intake also drops down and ultimately when the PI are off TPN, they don't get any IV supplemental L-arginine.

Why long term IV arginine not possible in preterm infants: In PI, the major cause of late onset infection (after 7 days of age) is central line related infection that is why central line is taken out as soon as infant reaches full feed.

Why oral citrulline: Enteral feeds (formula as well as breast milk) is poor source of arginine. Once PIs are on full enteral feed, an enteral feed is the only source of arginine. Interestingly, 40% of enteral arginine gets metabolized by arginase enzyme present in intestine. We speculate that plasma levels of arginine drop once TPN is discontinued and infants are on full feeds. Oral L-arginine has poor bio-availability that is why oral L-arginine supplementation does not increase blood levels of arginine. Since oral citrulline has high bioavailability, the best way to increase serum arginine levels is by oral citrulline supplementation. Oral supplementation of L-citrulline in preterm infants once they are off TPN will likely to increase arginine levels and NO production.

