## 3.0 Inclusion/Exclusion Criteria

Inclusion criteria - Subjects must meet all of the inclusion criteria in order to be eligible to participate in the study.

1. Infants  $\leq$  30 weeks' gestational age born at UTMB, Galveston.

2. Parents have provided informed consent/assent in a manner that is approved by the IRB

The reason for the inclusion of such a vulnerable population is that BPD is primarily a disease of premature infants and PH is a common complication of BPD. It is also a condition with high mortality and there still exists significant confusion over appropriate management. Being a randomized controlled trial, the study does add certain risks to the subjects: frequent blood draws (minimized by using discarded blood and urine samples) . Since diagnosis and management of BPD\_PH is not currently standard of practice, we will not be withholding any beneficial therapy. The present research protocol will not interfere in the management of the preterm infants as treating neonatal team will be taking all management decisions. All risks will be explained to the parents and written informed consent will be obtained from the parents of all subjects.

Exclusion criteria - Subjects meeting any of the exclusion criteria at baseline will be excluded from study participation.

1. Known congenital or chromosomal anomalies.

2. Congenital heart disease affecting cardio-respiratory system (other than PDA, PFO or ASD)

3. NEC, sepsis, or any condition requiring surgery prior to recruitment

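### Every group receives L-citrulline, so the paired pre/post t-test describes change over the week but cannot by itself attribute a rise to the drug

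*Combined protocol and SAP*

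**What the plan says.** Specific Aim 1 (section 2.0) sets out to test whether enteral supplementation "is effective in increasing plasma L-arginine and L-citrulline concentrations". The primary outcome in section 9.0 is "Increase in plasma L-citrulline levels and increased NO production". Both are statements about a rise.

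The same section says: "There will be 3 study groups in this Phase I trial". All three are active doses, with 14 infants each and 42 in total (section 4.0). The Background leaves a placebo-controlled trial for the future. Section 3.0 nevertheless introduces the study's risks with the words "Being a randomized controlled trial".

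Two analyses are named for the primary variables at the end of section 9.0. Between groups, "the one-way ANOVA will be used to analyze differences amongst the 3 treatment groups from day 0 and day 7". Within infants, "Paired T-test will be used to evaluate differences pre-and post-treatment in individual subjects". Section 9.0 also lists linear models and repeated-measures ANOVA, without tying either to an endpoint.

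On the untreated course, the Background offers one statement: "We speculate that plasma levels of arginine drop once TPN is discontinued and infants are on full feeds". Section 5.0 delays the start of study drug until the infant has had at least 3 days without TPN, to keep intravenous arginine from interfering. Blood is taken at Day 0 and Day 7.

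**The concern.** A pre/post change in a treated group is the sum of the drug effect and any change that would have occurred anyway. With no untreated infants followed over the same week, the paired test cannot tell these apart. The between-dose ANOVA asks whether the doses differ, which is a separate question, and the plan does not say which of the two analyses decides Aim 1.

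A significant paired test could therefore be reported as evidence that citrulline raised levels when only time had passed. A drug effect offset by a natural fall could equally be reported as absent. The Background says the results will inform a later placebo-controlled trial, so either error would carry forward.

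**Working it through.** **The plan's own figure.** Section 4.0 states power 0.80 for a one-way ANOVA with 3 groups of 14, effect size f = 0.5 and α = 0.05. The noncentrality is f²N = 0.25 × 42 = 10.5 on 2 and 39 degrees of freedom, which gives power 0.803. The stated figure reproduces. It belongs to the ANOVA; the documents give no power for the paired test.

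**What each analysis estimates.** Let δ_g be the drug effect on the change in dose group g, and τ the change over the week that would occur without drug, taken as common to all groups.

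- Paired test in group g: expected mean change = δ_g + τ.
- Difference between groups g and h: (δ_g + τ) − (δ_h + τ) = δ_g − δ_h.

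So τ stays in the first and cancels in the second. In a model for Day 7 values with Day 0 and dose as predictors, τ goes into the intercept and leaves the dose slope alone.

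**Illustration of the paired test under drift alone.** Inputs: n = 14 (section 4.0), two-sided α = 0.05 (section 9.0), δ_g = 0. The drift d, in SDs of the within-infant change, is an assumption, because the documents give no untreated trend. The test statistic follows a noncentral t with 13 degrees of freedom and noncentrality d√14. The critical value is 2.160.

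| Assumed drift d | Noncentrality d√14 | Two-sided rejection, n = 14 |
|---|---|---|
| 0 | 0 | 5% |
| 0.25 | 0.94 | 14% |
| 0.5 | 1.87 | 41% |
| 0.75 | 2.81 | 74% |

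If the paired test were pooled over all 42 infants, which the plan does not say, the last three figures would be 35%, 89% and above 99%.

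**Direction.** With an upward drift, nearly all of these rejections are false rises. With a downward drift of 0.5 SD, the chance of a false rise is below 0.1%, and the harm is the reverse. For example, a real drug effect of +0.5 SD would alone be detected with probability 41%; a drift of −0.5 SD brings the net change to 0 and the rejection rate back to 5%.

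**Scale.** Take the 4 µmol/L SD that section 9.0 expects for citrulline at the low and medium doses, and assume a Day 0 to Day 7 correlation r. The SD of the change is 4√(2(1 − r)). At r = 0.5 this is 4 µmol/L, so a 2 µmol/L upward drift is 0.5 SD and gives a false rise 41% of the time at n = 14. At r = 0 and r = 0.8 the figures for the same 2 µmol/L are 23% and 78%.

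**How much the dose contrast can carry.** Section 9.0 expects citrulline means of 19, 21 and 45 µmol/L with SDs of 4, 4 and 5. On those figures the three-group ANOVA has power near 1, almost all of it from the high dose. Low against medium is a difference of 2 with SD 4, or 0.5 SD, and a two-sample t-test with 14 per group has power of only 0.25.

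**The case against.** The strongest reply is that the plan already has a concurrent comparison. The efficacy sample size is built on the three-group ANOVA, that analysis is named before the paired test, and section 9.0 openly describes a single-center pilot dose-ranging study. This stands in part: the remedy re-ranks and sharpens analyses already foreseen. But the plan does not say that the Aim 1 claim rests on the dose contrast, and the ANOVA sentence names no baseline adjustment.

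A reader might infer that TPN washout and maturation are known to shift these values during the study week, so that a rise would be an artefact. The documents do not support this:

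- The TPN statement is labelled as speculation, concerns arginine only, and predicts a fall. Residual washout would work against finding an arginine rise.
- No TPN effect on citrulline, the plasma measure named in the primary outcome, is described.
- Section 5.0 requires at least 3 days off TPN before dosing, expressly to limit this interference. It does not settle whether levels are stable afterwards. The text ties the condition to the start of dosing and the baseline sample to the Tuesday after full feeds, so whether Day 0 blood always follows 3 TPN-free days should be clarified.
- No maturation trend is given for any of the primary variables.

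A reader might also infer that the dose contrast is fully protected by randomization. It is not: the example in section 4.0 is a fixed 1-2-3 rotation by order of entry, so the next assignment is predictable.

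The randomized-controlled-trial label appears in a paragraph about risk and drives no analysis. Correcting it is clerical.

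**Conclusion.** The point holds as one of attribution. Followed as written, the paired test would credit any change over the week to the drug, while Aim 1 and the primary outcome claim an increase. The conclusion needs no particular direction of drift; it follows from the absence of untreated infants.

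The 14%, 41% and 74% show how sensitive the test is to drift. They do not estimate what will happen in this trial, because they rest on assumed drifts and no drug effect. Cancellation in the dose contrast rests on the drift being common to the three groups, which concurrent enrolment makes reasonable but a predictable rotation does not guarantee.

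**What to change.** In the analysis text at the end of section 9.0:

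1. Name as the primary Aim 1 analysis an ANCOVA of the Day 7 value on the Day 0 value and dose, with a linear dose trend, in place of the unadjusted one-way ANOVA. Apply it to the primary variables already listed: plasma citrulline and arginine, and urinary nitrite and nitrate.
2. Report the pre/post change in each dose group as a mean with a 95% confidence interval, labelled uncontrolled, and draw no efficacy conclusion from the paired test.
3. Describe the analysis as a concurrent dose comparison, and state that allocation by rotation does not give it the full protection of randomization.
4. In section 3.0, replace the controlled-trial label with a description of a dose-ranging study without an untreated group.

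All Day 0 and Day 7 values are already collected, so the change adds no arm, infant, sample or procedure. The cost is in the claim. A rise that increases with dose would support a drug effect; a rise of similar size at all doses could be described but not firmly attributed to L-citrulline.
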